 - a. [Alternative should there be any issues with the camera or the patient must get out of the car]: The patient will take the completed test packet, place it back in the pouch and under the windshield. The HCW will take the packet and remove the **Consent Form** and **Multiple choice questionnaire form**, check if it is completed (if ask the patient), and place all remaining materials in a biohazard box for destruction. The Consent form and the Questionnaire will be digitalized (scan or photographed) and linked with EPIC so as to be compared to the PCR test results.
4. Information from the uploaded and **Multiple choice questionnaire form** will be entered by a person authorized to access the information into a table that includes:
 - a. Unique identifier
 - b. Gender
 - c. Age band (10 year)
 - d. Y/N to patient self-identified new loss of smell or taste
 - e. Y/N to patient response to "things in the last year smell different"
 - f. Y/N to patient self-identified blocked or stuff nose
 - g. Individual answers on the 5 window smell test
 - h. RT-PCR results for SARS-CoV-2 (+, - or Inconclusive)
 - i. Any other tests for COVID19 (CT or Serological) if given
5. The data will be analyzed in the following fashion:
 - a. Patients that report a blocked or stuffy nose will be excluded from the main analysis (as COVID-19 loss of smell is not due to nasal congestion); but will be analyzed separately to see how this would confound any interpretation.
 - b. Patients that are denoted SARS-CoV-2 "inconclusive" will be excluded from the main analysis; but will be separately analyzed to see if they colocalize with normosmia or anosmia.
 - c. Patients will be split into SARS-CoV-2 positive and negative. As the negative pool is likely to be much larger it will be statistically matched by gender and age profile (potentially with larger bands – e.g. 20 year, depending on the sample size)

- d. The + and - SARS-CoV-2 groups individual performance on the smell test (score 0-5) will be plotted as a histogram. A cutoff will best be chosen to segregate people with normosmia and anosmia (e.g. score = 2 or 3).
- e. False Positives (FP) and False Negatives (FN) will be identified and used to measure the selectivity and sensitivity, respectfully.
- f. Based on the statistical performance (see Table 1) we will determine when we have enough patients to complete the study with a given value of precision.

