6.4.2 Sample Size Considerations

Upon consultation with Yale biostatisticians Profs. [name] and [name], based on our sampling they calculated the following table to shows the precision of sensitivity/specificity measurements for different sample sizes (Table 1). For example, the 95% confidence interval for 90% sensitivity with 100 subjects ranges from 82 to 95% , but if we have 400 subjects, the confidence interval ranges from 87 to 93% (about +/- 3%). Thus the number of participants will be guided by statistical analysis of the data. A minimal estimate is ~100 outpatients that are SARS-Co-V2 positive so as to have good confidence intervals. Here we presume to have at least 100 age/gender matched SARS-Co-V2 negative subjects. If there are 3:1 SARS-Co-V2 negative to SARS-Co-V2 positive then ~400 outpatients (300 +100) will be tested. For the more exploratory testing with asymptomatics we will limit the study to up to 250 HCW. If the results are encouraging with a loss of smell in asymptomatic the sample size could be increased to increase the precision, as done in the outpatient cohort.

Table 1 (replicated from before): Sample Size Calculations (Width of a 95% confidence interval around the proportion).

*Denominator is those that are COVID+ for sensitivity and those that are COVID- for specificity

Sens/Spec	Sample Size for Denominator*						
	100	150	200	250	300	350	400
0.50	0.20	0.17	0.14	0.13	0.12	0.11	0.10
0.60	0.20	0.16	0.14	0.13	0.11	0.11	0.10
0.70	0.19	0.15	0.13	0.12	0.11	0.10	0.09
0.80	0.17	0.13	0.12	0.10	0.09	0.09	0.08
0.90	0.13	0.10	0.09	0.08	0.07	0.07	0.06

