6.4.3 Planned Analysis

6.4.3.1 Primary Analyses

Loss of smell in outpatients will be compared to the presence of SARS-CoV-2 coronavirus, as determined by RT-PCR. Key metrics that will be statically evaluated and done with support of YCCI and Yale biostatisticians Profs. [name] and/or [name] Sensitivity are:

- Sensitivity
- Specificity
- Accuracy
- Repeatability

- Other parameters that will be considered are the Area under the Curve (AUC)

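### Step 5c age/sex-matches the PCR-negative outpatients before specificity is calculated; primary specificity should use all eligible negatives, and the passages should agree on that

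*Combined protocol and SAP*

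**What the plan says.** Section 6.1.3 has all eligible drive-through subjects tested, and section 5.3.2 requires a same-day PCR. Section 6.3, step 5, then gives the order of analysis for outpatients:

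- 5a and 5b take stuffy-nose and PCR-inconclusive patients out of the main analysis. Section 6.4.5 separately removes tests with missing olfactory data.
- 5c splits patients by PCR result and says of the negatives: "As the negative pool is likely to be much larger it will be statistically matched by gender and age profile". Ten-year age bands are recorded (step 4c), but matching may proceed "potentially with larger bands – e.g. 20 year, depending on the sample size".
- 5d uses the two groups for the plot and the cutoff: "groups individual performance on the smell test (score 0-5) will be plotted as a histogram".
- 5e: "False Positives (FP) and False Negatives (FN) will be identified and used to measure the selectivity and sensitivity, respectfully". I read selectivity here as specificity.
- 5f relies on Table 1: "we will determine when we have enough patients to complete the study with a given value of precision".

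On numbers, the documents give only floors. The Synopsis wants a matched negative group no smaller than the positive one, and section 6.4.2 says "Here we presume to have at least 100 age/gender matched SARS-Co-V2 negative subjects". The 3:1 figure there (300 + 100) is a conditional recruitment forecast, not a matching ratio.

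Two other passages do not mention matching. Section 6.4.3.1 says "Loss of smell in outpatients will be compared to the presence of SARS-CoV-2 coronavirus, as determined by RT-PCR". The Table 1 footnote says "Denominator is those that are COVID+ for sensitivity and those that are COVID- for specificity".

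**The concern.** The reason 5c gives for matching is that the negative pool is large. For specificity that is no reason to match: it is estimated within the PCR-negatives, and more of them only helps. Matching can be useful for comparing the two groups' score distributions, because it removes age and sex differences between them. Applied before the false-positive count, it changes what specificity describes, from the eligible negatives who came for testing to negatives re-mixed to look like the positives. If it is done by dropping people, it also discards data already collected.

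The passages leave the set open. Step 5c is the only one that says how to handle the negatives remaining after 5a, 5b and 6.4.5, and in step order its output feeds 5d and 5e. The footnote and 6.4.3.1 can be read as using all negatives. Specificity and accuracy are both primary outcomes, and 5f uses Table 1 to judge when enough patients are in. The choice of negatives therefore affects a headline estimate and the count that is read against the precision table.

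**Working it through.** **1. Reproduce the plan's precision figures.** Inputs: proportion 0.90 with n = 100 and n = 400 (section 6.4.2). The exact (Clopper-Pearson) 95% interval for x out of n runs from the 0.025 quantile of Beta(x, n−x+1) to the 0.975 quantile of Beta(x+1, n−x).

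- 90/100: 0.8238 to 0.9510. The plan states 82 to 95%.
- 360/400: 0.8663 to 0.9276. The plan states 87 to 93%.

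This method matches 34 of the 35 cells of Table 1. The exception (0.60, n = 250) computes to 0.1248 against a printed 0.13. It is therefore the right yardstick.

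**2. Precision if negatives were dropped.** Take the conditional 300-negative, 100-positive scenario and suppose, which the plan does not say, that matching discards negatives to reach a fixed ratio.

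| Specificity | 100 kept (1:1) | 200 kept (2:1) | all 300 |
|---|---|---|---|
| 0.90, interval | 0.824–0.951 | 0.850–0.938 | 0.860–0.932 |
| 0.90, width | 0.127 | 0.088 | 0.071 |
| 0.80, width | 0.165 | 0.115 | 0.094 |

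At 0.90 the ratio of widths to the full set is 0.1272/0.0712 = 1.79 at 1:1 and 0.0881/0.0712 = 1.24 at 2:1. If all negatives are kept or weighted, no count is lost. Weighting can still cost some precision, by an amount that the documents do not let one calculate.

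**3. Shift from changing the age/sex mix.** With two strata, and matching that balances them exactly, the change in specificity is (difference in stratum share between negatives and positives) × (difference in specificity between strata). The documents give neither input, so these are assumed ranges:

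- 0.10 × 0.05 = 0.005
- 0.20 × 0.10 = 0.02
- 0.30 × 0.20 = 0.06

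The direction can be either way. For scale, the half-width with all 300 negatives at 0.90 is 0.0712/2 = 0.036. If the false-positive rate does not vary by age or sex, the shift is zero.

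**4. Accuracy and the cutoff.** Accuracy is the average of sensitivity and specificity weighted by the numbers of positives and negatives, so it depends on how many negatives remain. With assumed sensitivity 0.70 and specificity 0.90:

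- 1:1: (0.70 + 0.90)/2 = 0.80
- 3:1: (0.70 + 3 × 0.90)/4 = 0.85

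Section 5.2.1 allows the cutoff to be chosen on accuracy, so the ratio can change the choice. Assume one cutoff with sensitivity/specificity 0.80/0.80 and another with 0.60/0.90. At 1:1 the first wins (0.80 against 0.75). At 3:1 the second wins ((0.60 + 2.70)/4 = 0.825 against 0.80).

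**5. Which count goes into 5f.** In the 300 + 100 scenario at specificity 0.90, Table 1 reads 0.07 for all negatives and 0.13 for 100 matched ones. Step 5f does not say which applies.

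**The case against.** The strongest reply is that nothing in the plan commits it to losing data. Matching to a profile can be done by weighting or frequency matching, the stated numbers are minimums, and even 100 negatives give the width that Table 1 prints. This stands. A reader might infer that 200 of 300 tested negatives will be thrown away, or that a precision target is missed; the documents support neither.

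The reply continues that bias has not been shown. This also stands: a shift needs both a false-positive rate that varies with age or sex and a difference in mix between the PCR groups, and the documents give data on neither.

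Third, an all-negatives reading is available in the footnote and in 6.4.3.1. So it would be too strong to say that the plan rules out an all-negatives specificity, or that 5c is its only data-handling rule, since 5a, 5b and 6.4.5 are explicit as well. What remains is that 5c alone addresses the negatives left after those exclusions, the Synopsis and 6.4.2 also speak of matched negatives, and nothing says which reading governs.

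Finally, an age- and sex-comparable specificity is not invalid, and at a fixed cutoff matching the negatives leaves sensitivity untouched. Both are true. They support keeping the matched comparison alongside the main estimate, but do not make it the better basis for primary specificity.

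**Conclusion.** The point holds as a choice of method, together with wording that does not agree clearly across sections. Followed in step order, 5c to 5e give a specificity for negatives re-mixed to the positives' age and sex profile, for a reason (pool size) that does not call for it. Using all eligible negatives is the better primary estimate and costs almost nothing.

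The size is modest and conditional. The 1.79-fold wider interval at specificity 0.90 needs a 3:1 pool, discarding, and a 1:1 ratio all at once. It is avoidable inefficiency, since the result still meets Table 1's 0.13. The mix shift of 0.005 to 0.06 rests wholly on assumed inputs and could be zero. A reader might conclude that reported specificity will be biased; the documents do not establish that. The change should be made before analysis, but the point does not put the study's validity in doubt.

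**What to change.** In section 6.3, steps 5c to 5f, and in section 6.4.3.1, use the same wording to state that:

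- primary specificity, and the negative count read against Table 1, come from all PCR-negative outpatients remaining after 5a, 5b and 6.4.5;
- the age/sex-matched or weighted comparison is a supporting analysis, with its method (drop or weight, ratio, band width, selection rule) fixed in advance;
- the set used to choose the cutoff is named in advance;
- accuracy is reported with the negative-to-positive ratio to which it refers.

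Specificity by sex and broad age group may be shown descriptively. The seven recorded bands would be thin: 300/7 is about 43 negatives per band if evenly spread, and about 21 if also split by sex.

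The cost is wording and a little more analysis, with no new patients or data. The downside is that the full-set groups are not balanced on age and sex, which can affect the histogram, AUC and cutoff. The supporting analysis is kept for that reason.

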- Waveny LifeCare Nursing Home in New Canaan, CT
 - Point Pleasant Nursing Home, Bradenton, Florida
 - Westminster Winter Park/Baldwin Park Nursing Home

Primary Outcome Variables

The subject's score on using the olfactory device will be compared to the PCR results

(SARS-CoV-2 negative or positive) on COVID19 outpatients. As the smell test has a variable scale (0-5) the ideal cutoff will be determined to maximize these factors:

- Sensitivity
- Specificity
- Accuracy

The score with the olfactory device will also be compared to subjects' response to the question "Do you have a new loss of smell or taste?" (current standard). Repeatability will also be examined in a test-retest score conducted within 24 hours with a second device in which the sequence of the odorants is altered.

Secondary and Exploratory Outcome Variables (if applicable)

We will determine if 'asymptomatic' SARS-CoV-2 positive subjects experience a partial loss of smell (hyposmia) and if so determine the fraction of subjects in which this occurs. Sensitivity, specificity and accuracy will be measured.

Visit Schedule Table (Optional). N.A.

Study Flow Chart (optional). N.A.

Abbreviations

Abbreviation	Explanation
HCW	Health Care Worker
UPSiT	University of Pennsylvania Smell Identification Test
COVID-19- or COVID-19+	Negative for COVID-19 virus (as determined by RT-PCR) or Positive for COVID-19 virus (as determined by RT-PCR)
ICU	Intensive Care Unit
IFRA	International Fragrance Association
CPSIA	Consumer Product Safety Information Act

Glossary of Terms

Glossary	Explanation
Anosmia	Full loss of ability to smell odors
Hyposmia (aka. Microsmia)	Partial loss of ability to smell odors
Normosmia	Normal olfactory function and ability to smell odors (most people)
COVID-19	Disease associated with the SARS-CoV-2 coronavirus

Table of Contents

Synopsis.....	3
Primary Objective	3
Secondary Objectives (if applicable)	3
Study Duration.....	3
Study Design	3
Study Population	3
Number of Participants.....	4
Number of Study Sites	4
Primary Outcome Variables	4
Secondary and Exploratory Outcome Variables (if applicable).....	4
Visit Schedule Table (Optional)	4
Study Flow Chart (optional)	4
Abbreviations	5
Glossary of Terms.....	6
1 Introduction	10
1.1 Introductory Statement.....	10
2 Background.....	11
2.1.1 Device Preclinical Experience	11
2.1.2 Device Clinical Experience	11
2.2 Background/prevalence of research topic	11
3 Rationale/Significance	13
3.1 Problem Statement	13

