4.2 Primary Objective

The primary objective of this study is to validate the utility (sensitivity, specificity and accuracy) of a quantitative non-biased olfactory device for the rapid identification of SARS-CoV-2 infected subjects (as identified by PCR). The performance of the device will also be compared to the standard CDC patient query for ‘new loss of smell or taste’.

Secondary Objectives

The secondary objective is to test if SARS-CoV-2 positive ‘asymptomatic’ COVID-19 subjects may actually present with a mild or transitory defect in smell (hyposmia), which is revealed through our quantitative olfactory smell test.

5 Study Design

[figure not shown]

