5.2 Outcome Variables

5.2.1 Primary Outcome Variables

The subject's score on using the olfactory device will be compared to the PCR results (**SARS-CoV-2 negative or positive**) on COVID19 outpatients. As the '*u-Smell it*' test has a variable scale (0-5) the ideal cutoff will be determined to maximize any one (or combination) of these factors:

- Sensitivity

- Specificity
- Accuracy

We will compare the performance of the smell test to the current CDC metric of self-described assessment of smell loss (the de facto standard – e.g. “I have a new loss of smell or taste”) in terms of sensitivity, specificity and accuracy. Repeatability will also be examined in a test-retest score conducted within 24 hours in a random subset of 25 asymptomatic HCW with a second device in which the order of the odorants is altered.

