5.2.2 Secondary and Exploratory Outcome Variables (if applicable)

We will determine if ‘asymptomatic’ SARS-CoV-2 positive subjects experience a partial or transitory loss of smell (hyposmia) and if so determine the fraction of subjects in which this occurs. Sensitivity, specificity and accuracy will be measured.

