- g. If a subject fails the smell test (hyposmia or anosmia) but is SARS-CoV-2 negative, yet has other symptoms suggesting being positive for COVID19, we will consider re-testing the subject in 2-3 days by the PCR or serological assay in case the loss of smell precedes a PCR result, or the loss of smell extends past the point in which the viral titer is low and no longer picked up by PCR and would instead be detected by an antibody.

6. The treatment of asymptomatic people will follow an identical protocol with the following differences:
 - a. The study group would consist of high risk subjects that are determined to be positive to SARS-CoV-2 (yet asymptomatic) and the control group would be SARS-CoV-2 negative subject of matching age and gender.
 - b. The smell kit will be directly given to the subject and for HCW the test can be performed at their home.
 - c. There will be a variation of the test in which the order of the scents is altered so that the HCW subject can be re-tested.
 - d. The initial sample size is smaller as this study would firstly see if there was a significant increase of the fraction of anosmia or hyposmia subjects in COVID19+ asymptomatic individuals.

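### No score defines hyposmia, the secondary outcome; the only stated cutoff is normosmia versus anosmia, so the asymptomatic result depends on a cut left open

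*Combined protocol and SAP*

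**What the plan says.** - **Target.** The secondary objective (set out under 4.2) is whether asymptomatic positives "may actually present with a mild or transitory defect in smell (hyposmia), which is revealed through our quantitative olfactory smell test". The outcome in 5.2.2 is whether they "experience a partial or transitory loss of smell (hyposmia) and if so determine the fraction of subjects in which this occurs".
- **Definitions.** The Glossary separates hyposmia ("Partial loss of ability to smell odors") from anosmia ("Full loss of ability to smell odors"). Neither is tied to a score.
- **Rule.** In 6.3, step 5d plots the 0-5 scores of the positive and negative groups and then says: "A cutoff will best be chosen to segregate people with normosmia and anosmia (e.g. score = 2 or 3". It does not say whether the cutoff value itself counts as abnormal. Section 5.2.1 leaves the value open: "the ideal cutoff will be determined to maximize any one (or combination) of these factors".
- **Asymptomatics.** Step 6 says: "The treatment of asymptomatic people will follow an identical protocol with the following differences". None of the differences 6a to 6d sets a cutoff. Step 6d looks for "a significant increase of the fraction of anosmia or hyposmia subjects in COVID19+ asymptomatic individuals", and step 5g also treats hyposmia as failing the test.
- **Analysis.** Section 6.4.3.2 focuses on sensitivity and specificity, which both need a cutoff. The AUC is only to be considered, and it is listed under the primary analyses (6.4.3.1). Section 7.14 allows the asymptomatic part to be stopped if olfactory performance shows no difference.

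**The concern.** The secondary question concerns the middle of the scale, but the one classification rule is worded for its two ends. Steps 5g and 6d show that hyposmia is meant to count as abnormal, and no score puts that into effect. Two analysts following the text could report very different hyposmic fractions from the same data.

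Two things are at stake. A low cut could hide real mild loss and lead to use of the stopping option in 7.14. A cut chosen after the asymptomatic results are seen could make a difference look larger than it is. Separately, comparing a dichotomised fraction discards ordering that the recorded 0-5 score already holds.

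**Working it through.** **The plan's own figure.** The only calculated figures are the confidence-interval widths in Table 1 and the worked example beside it. Exact (Clopper-Pearson) 95% limits for 90% sensitivity are 82.4-95.1% at n=100 and 86.6-92.8% at n=400, which agree with the printed 82-95% and 87-93%. These figures do not bear on the cutoff: 2 or 3 is an example with no derivation.

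**Inputs from the protocol.** Five windows, score 0-5 (6.3). Asymptomatic sample about 100 positive and a similar number negative (5.3.1), or up to 250 healthcare workers in total (6.4.2). At least 30 asymptomatic positives at one nursing home (5.1.1).

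**Assumptions.** Score ~ Binomial(5, p), with p the chance of a correct answer per window. Partial loss p = 0.5 to 0.85; normal p = 0.92 or 0.95. Abnormal means score ≤ c. Two-sided 5% level, since the protocol states none.

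**Step 1: mild loss scored normal.** For p = 0.80:
- P(score ≤ 2) = 0.2⁵ + 5(0.8)(0.2⁴) + 10(0.8²)(0.2³) = 0.0003 + 0.0064 + 0.0512 = 0.058
- P(score ≤ 3) = 0.058 + 10(0.8³)(0.2²) = 0.058 + 0.205 = 0.263
- P(score ≤ 4) = 1 − 0.8⁵ = 0.672

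Share scored normal, over a range of p:

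| Abnormal if | p=0.5 | p=0.6 | p=0.7 | p=0.8 |
|---|---|---|---|---|
| ≤2 | 50% | 68% | 84% | 94% |
| ≤3 | 19% | 34% | 53% | 74% |
| ≤4 | 3% | 8% | 17% | 33% |

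**Step 2: effect on the reported fraction.** Suppose half of the positives are mildly affected (p = 0.80) and everyone else has p = 0.95. For p = 0.95 the abnormal shares are 0.1%, 2.3% and 22.6%. Positives scored abnormal:
- ≤2: 0.5(5.8%) + 0.5(0.1%) = 3.0%
- ≤3: 0.5(26.3%) + 0.5(2.3%) = 14.3%
- ≤4: 0.5(67.2%) + 0.5(22.6%) = 44.9%

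A true 50% is reported as about 3%, 14% or 45%. The last figure stands beside 22.6% among negatives.

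**Step 3: cost of a high cutoff.** With normal p = 0.92, the share of normals scored abnormal is 0.5% at ≤2, 5.4% at ≤3, and 1 − 0.92⁵ = 34% at ≤4.

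**Step 4: power.** Every positive has p = 0.85 and every negative p = 0.92, so the abnormal shares are 2.7% v 0.5%, 16.5% v 5.4% and 55.6% v 34.1%. Fisher's exact test at each cutoff, against Wilcoxon on the score, by simulation (accurate to a point or two):

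| Positives v negatives | ≤2 | ≤3 | ≤4 | Wilcoxon |
|---|---|---|---|---|
| 100 v 100 | 3% | 66% | 84% | 92% |
| 30 v 220 | 14% | 53% | 61% | 72% |

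The second row is an assumed split of the 250 workers (250 − 30 = 220).

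**The case against.** A reader might infer that the plan scores most partial loss as normal. The documents do not support that. Steps 5g and 6d put hyposmia on the abnormal side, the cutoffs are examples, and 5.2.1 would permit a cutoff of 4. In the table above, more than half is scored normal at ≤2 only when p exceeds 0.5, and at ≤3 only when p exceeds about 0.69. The protocol's own inpatient figures (2.2) point the same way: a cut catching only anosmia or severe loss would miss 98 − 58 = 40 points, or 40/98 = 41% of those with any dysfunction. That is substantial but not most, and the asymptomatic mix is unknown.

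A reader might also infer that a cutoff tuned in outpatients is imposed on asymptomatics. Step 6 can equally be read as choosing the cutoff again from the asymptomatic scores; the text does not settle it.

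Nor does 7.14 force a stop. It is permissive, names no cutoff, and can be read as referring to the full score. A well-placed cut can also perform well: at p = 0.80 v 0.92 with every positive affected and 100 per group, ≤3 gives about 98% power. Finally, the plan calls this part exploratory and already plots the full distribution.

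All of this stands, and it limits the point. It supplies neither a hyposmia score nor a named test of the full score.

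**Conclusion.** The concern holds as a gap in definition and a less efficient choice of test. The outcome is hyposmia, the only classification rule separates normosmia from anosmia, its direction is unstated, and its source for asymptomatics is open. That much rests on the text alone.

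The sizes rest on the binomial model. The share of mild loss scored normal runs from 33% to 94% across the three cutoffs at p = 0.80. The full-score test gains 8 points of power over the best of the three cutoffs (92% v 84%) and 89 over the worst (92% v 3%) at 100 per group, if every positive is affected. Different score distributions would change these figures but would not supply the missing definition. A false null leading to discontinuation is possible, not established. The change should be made; the exploratory status of this part makes it less than critical.

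**What to change.** - **Test.** For asymptomatics, make the secondary test a comparison of the full 0-5 score between PCR-positive and PCR-negative subjects: Wilcoxon, or proportional odds adjusted for age band and gender. Base any judgement of no difference under 7.14 on it.
- **Bands.** Before asymptomatic scores are compared with PCR status, fix score bands for normal, hyposmia and anosmia, with direction. Say whether they are the outpatient bands, and reconcile step 5d with 5g and 6d. A percentile rule in negatives is not enough by itself: at p = 0.92, 94.6% of normals score 4 or 5, so a rule set at the level 90-95% of them reach gives ≤3, which still scores 74% of mild loss (p = 0.80) as normal.
- **Reporting.** Give the hyposmia and anosmia fractions in positives beside the same fractions in matched negatives, so that the false-positive cost of a high cutoff is visible.

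Cost: protocol wording and one ordinal analysis of answers already recorded under step 4g. One drawback is that the ordinal test can be less powerful than a well-placed cutoff if only a few positives have marked loss. Reporting the banded fractions alongside it keeps that pattern in view.
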